1.0 BACKGROUND AND RATIONALE

1.1 Study Synopsis

Main Trial (ages 50-75)

This study assesses the effectiveness, feasibility, acceptability, and cost-effectiveness of mailed fecal immunochemical test (FIT) screening, compared to usual care, among patients aged 50-75 served by Roanoke Chowan Community Health Center (RCCHC) and Blue Ridge Health (BRH) who are due for colorectal cancer screening (CRC) according to US Preventive Services Task Force (USPSTF) guidelines for improving CRC screening rates. It includes formative work to develop and refine the intervention implementation and outcomes measurement, as well as a randomized controlled trial. We will work with RCCHC and BRH to identify up to 4,000 patients who are potentially eligible for CRC screening. Patients will be randomized to the following two arms: usual care (Arm 1) and mailed FIT plus up to two mailed reminders to complete the FIT (Arm 2). Current usual care at RCCHC and BRH consists of a visit-based FIT distribution approach. We hypothesize that we will observe higher CRC screening completion rates among patients assigned to study Arm 2. Our economic outcomes are the per-arm total costs and the incremental cost-effectiveness of intervention versus usual care arms, measured in cost per person screened for CRC.

Additional sub-study (ages 45-49)

This sub-study also will identify approximately 450 additional patients aged 45-49 served by RCCHC who are newly eligible for CRC screening because of updated USPSTF recommendations, which were recently revised in May 2021 to include this age group. We will work with RCCHC to identify the sample of patients aged 45-49 who are potentially eligible for CRC screening under these new recommendations. In this sub-study we will examine CRC screening (as measured by mailed FIT return rates), but not economic outcomes.

We will evaluate our mailed outreach intervention in this newly eligible age group in two ways: First, we will compare screening rates in this age group cohort at a single clinic before and after conducting mailed FIT outreach intervention. Second, we will conduct a nested trial conducted in this single site cohort to assess the impact of the appearance of the envelope that contains the FIT on FIT return. Patients will be randomized to one of two arms: an experimental arm (padded envelope with tracking label and sticker message) and an active comparator arm (plain envelope without tracking label or sticker message). Both arms will receive the same envelope contents (FIT and instructions) as described above. We hypothesize that we will observe higher FIT completion rates among patients assigned to the experimental arm.

1.2 Background

CRC is the third most common cancer diagnosis and the second leading cause of cancer death in the United States (U.S. Cancer Statistics Working Group, 2013). Screening is effective in reducing CRC incidence and mortality (United States Preventive Services Task Force et al., 2016), but CRC screening is underused. Although CRC screening has increased since 2002, current screening rates remain modest, with only 68% of age-eligible adults in North Carolina up-to-date with screening in 2012 (Centers for Disease Control and Prevention [CDC], 2013).

In North Carolina, as in many parts of the United States, screening is substantially underused in vulnerable and marginalized populations (CDC, 2013). CRC burden is particularly high in certain regions of the state. A recent study identified one such region (“hotspot”) in northeastern North Carolina with elevated CRC mortality rates compared to national averages (Siegel et al., 2015). Hertford County, in which RCCHC is located, is one of 11 counties in North Carolina that is included in this “hotspot.” This “hotspot” is a priority area for interventions to increase CRC screening. The western region of North Carolina, in which BRH is located, is a mountainous area characterized by rural, largely white, Appalachian communities as well as large and growing communities of Hispanic immigrants who work in the agricultural sector (e.g., the Christmas tree industry). Both regions afford a critical opportunity to address disparities in CRC screening and disease burden.

Increasing CRC screening among vulnerable populations will be crucial to reach the Healthy People 2020 and National Colon Cancer Roundtable goals of having 70.5-80% of the age-eligible population up-to-date with CRC screening (National Colorectal Cancer Roundtable, n.d.; Office of Disease Prevention and Health Promotion, 2014).

The United States Preventive Services Task Force (2016) recommends several stand-alone tests to screen for CRC, including colonoscopy every 10 years and fecal blood tests such as fecal immunochemical testing (FIT) annually, for patients ages 50-75 years, and more recently, patients ages 45-49 years (USPSTF, 2021). Further, the CDC Community Guide to Prevention recognizes several effective and cost-effective means of increasing CRC screening, including interventions to decrease structural barriers (such as mailed, at-home stool testing) (Sabatino et al., 2012). Mailed programs of FIT have shown promise as an effective means of increasing screening use, including for vulnerable populations. One program showed that a mailed FIT-based outreach program could increase screening by nearly 30 percentage points among vulnerable patients in a safety net system in Texas (Gupta et al., 2013). Several other studies have found mailed fecal testing programs to be effective in increasing screening rates in insured populations (Church et al., 2004; Kempe et al., 2012; Levy et al., 2012). However, researchers and experts attending a CDC-sponsored Mailed FIT Summit in June 2019 identified the challenge of getting patients to “open the envelope” (Gupta et al., 2020). Summit participants suggested making the

packaging eye-catching to increase the likelihood that patients will open the packet and respond. Additional research is needed to better understand how best to engage patients in mailed FIT outreach and prompt them to “open the envelope. To date, such programs have not been implemented and tested in North Carolina’s vulnerable populations.

Through this study, we will work with federally qualified health centers (FQHCs; RCCHC and BRH) to help increase the rate of CRC screening completion among their screening-eligible patients, including underserved adults. Approximately 54% of screening-eligible patients aged 50-75 at RCCHC are up-to-date with CRC screening, leaving about 46% ($n = \sim 3,100$) patients aged 50-75 due for screening and thus potentially eligible to be randomly selected for this study. Approximately 67% of screening-eligible patients aged 50-75 at BRH are up-to-date with CRC screening, leaving about 33% ($n = \sim 2,600$) patients eligible to be selected for this screening study.

In addition, we will work with RCCHC to promote uptake of CRC screening among their screening-eligible patients aged 45-49. We will enroll all patients who are aged 45-49 and meet study eligibility criteria. Based on a recent query of RCCHC’s EHR, there are approximately 450 patients aged 45-49 who currently are eligible for CRC screening. We will compare screening completion before and after mailed FIT outreach and will assess the impact of envelope appearance on FIT return.

1.3 Purpose and Rationale

Main Trial (ages 50-75)

Although the effectiveness of mailed FIT-based screening programs has been demonstrated within organized health systems (Daly et al., 2010; Levy et al., 2012), it is unclear whether this approach is effective, feasible, acceptable, and cost-effective in community health centers, which tend to be under-resourced. The purpose of this study is to assess whether a mailed FIT outreach program can improve CRC screening completion among patients aged 50-75 served by RCCHC and BRH. Using a randomized controlled trial study design, our study team will randomly assign patients to the following arms:

Arm 1 (control): Usual care

Arm 2 (intervention): Mailed FIT plus up to 2 reminder letters

We will compare the two arms on CRC screening completion rates. We will also assess and compare implementation outcomes for the intervention arm (Arm 2), including whether the mailed FIT outreach program was feasible, acceptable, and cost-effective.

Sub-study (ages 45-49)

In patients aged 45-49 (newly eligible per updated USPSTF recommendations), we will evaluate: 1) screening completion before and after the mailed FIT outreach, and 2) FIT return comparing two types of envelopes for the mailed FIT outreach.

To assess the effect of the two types of envelopes on FIT return, we will randomly assign patients to one of two arms as described below.

Arm 1 (experimental arm): FIT is packaged in a padded envelope with a sticker message (e.g., “Important information from your doctor”) and a United States Postal Service tracking label.

Arm 2 (active comparator arm): FIT is packaged in a plain white envelope without a sticker message or tracking label.

We will also conduct exploratory subgroup analyses to assess program reach, defined as the proportion and representativeness of patients who complete a FIT.

2.0 STUDY OBJECTIVES AND ENDPOINTS

2.1 Primary Objective (Aim 1)

Main Trial (ages 50-75)

The primary objective of this study is to assess the effectiveness of a mailed FIT outreach program on CRC screening completion in a community health center context in both northeastern and western North Carolina, by comparing the proportion of patients aged 50-75 years screened (as indicated by FIT or colonoscopy completion, assessed in the electronic health records [EHRs]), in the intervention arm and the control arm, 6 months post-intervention. Because both FIT and colonoscopy are viable CRC screening options and some patients may opt for a colonoscopy instead of the FIT, our measure of CRC screening completion includes both FIT and colonoscopy completion. We hypothesize that CRC screening completion rates will be higher among patients in Arm 2, compared to patients who received usual care in Arm 1.

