3.1 Inclusion Criteria

Individuals must meet all of the following inclusion criteria to participate in this study:

- 3.1.1 Main trial: Age 50-75 years; Sub-study: Age 45-49 years
- 3.1.2 At average risk for CRC (“average risk” is defined as those patients who do not have any of the following: history of CRC, colonic adenomas, family history of CRC, or diagnosis of inflammatory bowel disease)
- 3.1.3 No record of fecal occult blood test (FOBT)/FIT within the past 12 months or colonoscopy within 10 years, sigmoidoscopy within 5 years, barium enema within 5 years, or computed tomography (CT) colonography within 10 years of the EHR query date
- 3.1.4 No record of any CRC diagnosis or total colectomy
- 3.1.5 Active patient (seen within the past 18 months) of RCCHC or BRH

Patients invited to participate in an interview will meet three additional inclusion criteria: aged 50-75; be assigned to study Arm 2 in the Main Trial; and have a positive (abnormal) FIT result as a participant in the screening program. We will not interview participants who are aged 45-49.

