4.0 STUDY PLAN

4.1 Main Trial Schema

This trial will enroll up to 4,000 patients aged 50-75 years who are not up-to-date with CRC screening. The primary purpose of this study is to assess the effectiveness of mailed FIT outreach on CRC screening completion in a community health center context in both northeastern and western North Carolina, by comparing the proportion of patients screened across two study arms.

All participants assigned to Arm 2 will be eligible to receive two intervention rounds, scheduled about 54 weeks apart. These two intervention rounds will allow us to longitudinally assess adherence to the United States Preventive Services Task Force recommendations for annual screening with FIT (see 1.2). Arm assignment will remain the same across both intervention rounds. Patients will be

included in the second intervention round if they continue to meet the study's IRB-approved inclusion criteria for age, risk, screening history, CRC or colectomy history, and active patient status (seen within the past 18 months). In accordance with clinical recommendations, patients who receive a positive (abnormal) FIT result in the first round will not be included in the second round of FIT mailings (they will not be mailed a FIT).

We anticipate that the approximate time for the study team to complete each of the two rounds of study mailings will be 3 months, and patients' active participation during each round will last from 4 weeks (for patients with a FIT negative result and needed few, if any, reminders to complete the FIT) up to 6 months (for patients with a positive FIT result who need a follow-up colonoscopy, and needed several reminders to complete the FIT). For each round, we will assume that patients who have not completed screening (FIT, screening colonoscopy, or follow-up colonoscopy) after 6 months following the FIT kit mailing, do not intend to do so. We will randomly select an equal number of control group participants to correspond to each mailing wave for intervention participants, and will track both intervention and control participants for the same time period (from Introductory Letter mailing to 6-months post-mailing).

[figure not shown]

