4.3.6 Data Collection

REDCap database: RCCHC and BRH will securely transfer patient information from the EHR to a secure SharePoint folder at UNC. A UNC research assistant will then upload the data to a REDCap database (developed based on two previous completed or ongoing studies). Data will include, but not necessarily be limited to, patient name, age, sex, race/ethnicity, mailing address, identified primary care provider, and if possible, the number of visits within the past 18 months with that provider. The study team has fully executed data use agreements in place with each FQHC. Designated approved members of the research team members will use the REDCap database to document whether patients were mailed a FIT kit and to track the status of FIT kit completion (yes or no), test result (positive or negative), contact with patients who have positive results (yes or no), and receipt of navigation support for colonoscopy (yes or no), including referrals for no-cost follow-up colonoscopy (yes or no) and transportation services (yes or no). Approved members of the UNC research team will also document in the REDCap database whether patients call to report they are ineligible for FIT screening per their screening and relevant medical history (e.g., already completed CRC screening elsewhere, have a medical history that places them at higher than average risk for CRC).

EHR: Each CHC will specify, train, and credential members of the UNC research team to conduct a manual review of participant EHRs 6 months or more after randomization to determine whether patients completed any CRC screening test (FIT, colonoscopy, flexible sigmoidoscopy, Cologuard) and, if so, the test result. As mentioned in the preceding paragraph, these data will be entered directly into the REDCap database by IRB-approved UNC staff members for analysis.

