7.3 Data Analysis Plans

Main Trial

Our main statistical test for primary and secondary outcomes will be a Mantel-Haenszel chi-squared test, adjusted for recruitment site (FQHC). If there are important differences between the control and intervention arms across baseline variables known to be associated with the outcome being tested, we will also then use multiple logistic regression, adjusting for the additional baseline variables. One-sided tests will be used for the primary and secondary outcomes because we expect active interventions will lead to more favorable results compared to usual care.

7.3.1 Aim 1

For Aim 1, the main outcome of interest is the proportion of the sample completing FIT kits among those to whom the materials are mailed. We refer to this metric as the “proportion screened.” Using a 1:1 randomization approach, up to 2,000 RCCHC patients and up to 2,000 BRH patients will be randomized to each study arm (Arm 1-usual care; Arm 2-introductory letter + mailed FIT + 2 follow-up reminder letters).

Aim 1 analytic approach: Our primary analysis will be a crude comparison of proportions of completed CRC screening at 6 months post-FIT mailing for the mailed FIT plus reminder arm vs. the usual care arm using a one-sided Mantel-Haenszel chi-squared test, controlling for recruitment site (FQHC) and insurance status. As stated in the overview, we will also, if necessary, conduct a multiple logistic regression analysis. We will also compare the proportion screened between the mailed FIT plus reminder arm vs. the usual care arm for each of the four insurance status groups, using a one-sided Mantel-Haenszel chi-squared test, controlling for recruitment site, conducted at the 0.0125 significance level.

7.3.2 Aim 2

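### The primary endpoint counts only FIT or colonoscopy, the chart review collects more tests, and the analysis section defines the outcome in two further ways; one definition is needed for both arms

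*Combined protocol and SAP*

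**What the plan says.** Section 2.1 sets the primary endpoint as screening found in the health record at 6 months and states that "our measure of CRC screening completion includes both FIT and colonoscopy completion". Its reason is that some patients may choose colonoscopy over the mailed test. Section 4.1 uses the same scope when it refers to "patients who have not completed screening (FIT, screening colonoscopy, or follow-up colonoscopy) after 6 months following the FIT kit mailing".

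Section 4.3.6 asks chart reviewers for more: "whether patients completed any CRC screening test (FIT, colonoscopy, flexible sigmoidoscopy, Cologuard) and, if so, the test result".

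The entry criteria use a third list. Besides FOBT/FIT in the past 12 months, 3.1.3 treats as not due anyone with "colonoscopy within 10 years, sigmoidoscopy within 5 years, barium enema within 5 years, or computed tomography (CT) colonography within 10 years". Section 4.1 applies the screening-history criterion again before round 2.

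Section 7.3.1 adds two versions. It says that "the main outcome of interest is the proportion of the sample completing FIT kits among those to whom the materials are mailed", then describes the primary analysis as a comparison of completed CRC screening at 6 months, with no tests listed. Sub-study outcome 1 in section 2.2 counts any CRC screening. Nothing says how a sigmoidoscopy or Cologuard found on chart review is scored in the main trial's primary analysis.

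**The concern.** The question is whether outreach gets more people screened. An endpoint limited to two tests answers it only if other tests are negligible or equally common in the two arms. Arm 2 is sent a FIT, which counts. If some recipients use it in place of a sigmoidoscopy or Cologuard they would have had anyway, the endpoint records a gain although no extra person was screened. That would raise the arm difference, lower the apparent cost for each extra person screened (Aim 3), and push in the direction of the one-sided test.

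Separately, the plan does not settle which outcome is analysed. With several definitions in the text and the wider data already collected, the choice could be made after the results are known.

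**Working it through.** **1. The lists side by side**

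| Test | Endpoint (2.1, 4.1) | Chart review (4.3.6) | Makes patient not due (3.1.3) |
|---|---|---|---|
| FIT | yes | yes | yes, 12 months |
| Colonoscopy | yes | yes | yes, 10 years |
| Sigmoidoscopy | no | yes | yes, 5 years |
| Cologuard | no | yes | not listed |
| FOBT other than FIT | no | not named | yes, 12 months |
| Barium enema | no | not named | yes, 5 years |
| CT colonography | no | not named | yes, 10 years |

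Sigmoidoscopy is the only test outside the endpoint that is on both other lists. A round-1 sigmoidoscopy patient is a non-responder under 2.1, yet not due at the round-2 query. Cologuard is collected as an outcome but is silent at entry.

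The FIT-kit metric in 7.3.1 is conditioned on being mailed a kit. Section 4.3.7.1 says main-trial controls are not contacted, so the metric has no value in Arm 1.

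**2. The plan's own sample size**

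Inputs from 7.2: 17% and 25%, one-sided alpha 0.0125, power 80%. With mean rate 0.21:

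n = [2.2414 × √(2 × 0.21 × 0.79) + 0.8416 × √(0.17 × 0.83 + 0.25 × 0.75)]² / 0.08² = 491.5, so 492 per arm per stratum.

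492 × 2 × 4 = 3,936. The plan's figures reproduce, and power at 492 is 80.05%.

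**3. Size of the bias**

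Let s1 and s2 be the shares of Arm 1 and Arm 2 screened only by an omitted test. The scored difference exceeds the any-test difference by s1 − s2. If a fraction d of these tests is displaced, s2 = (1 − d) × s1 and the excess is d × s1.

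The documents give neither s1 nor d. Assuming s1 = 1% to 3% and d = 0 to 1:
- smallest: 0 × s1 = 0 points
- largest: 1 × 3% = 3 points

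Each 1% is about 20 of up to 2,000 patients per arm.

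For Aim 3, if incremental cost is held fixed and the scored difference is 8 points, the reported cost for each extra person screened is (any-test difference)/8 of the any-test value: 8/8 = 1 with no displacement, 7/8 = 0.875 with a 1-point excess, 5/8 = 0.625 with a 3-point excess.

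**4. Effect on a false claim**

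Suppose any-test completion is truly 20% in both arms, with 2,000 per arm. One-sided alpha of 0.05 is assumed, because none is stated for the overall test.

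| s1 / s2 | Scored rates, Arm 1 vs Arm 2 | Chance of rejection |
|---|---|---|
| equal | equal | 5% |
| 1% / 0.5% | 19% vs 19.5% | about 11% |
| 2% / 1% | 18% vs 19% | about 20% |
| 3% / 0% | 17% vs 20% | about 79% |

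The last row is the extreme corner of the assumed range.

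**5. Power under an any-test endpoint**

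This reads 17% and 25% as FIT-or-colonoscopy rates and adds the omitted tests.

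| s1 / s2 | Difference, points | n per arm per stratum | Power at 492 |
|---|---|---|---|
| 1% / 1% | 8 | 509 | 78.6% |
| 3% / 3% | 8 | 541 | 75.8% |
| 1% / 0.5% | 7.5 | 574 | 73.0% |
| 2% / 1% | 7 | 676 | 65.1% |
| 2% / 0% | 6 | 905 | 51.2% |
| 3% / 0% | 5 | 1,325 | 35.8% |

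The overall comparison at 2,000 per arm keeps at least 98% power in every scenario tried (one-sided 0.05 assumed).

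**The case against.** FIT-or-colonoscopy is a prespecified choice with a stated reason. Section 1.1 describes usual care at both centers as FIT given at visits, so controls are mainly offered a test that counts. No section says that Cologuard, guaiac FOBT or CT colonography is in routine use at either center. The scoring rule applies to both arms. The Arm 2 letters and education sheet (4.3.3) could also prompt other tests, which would work against the displacement argument. All of this stands, and it limits the size of the problem.

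A reader might infer more: that the endpoint miscounts controls specifically, because they choose freely among all tests, and so inflates the effect by some definite amount above zero. The documents do not support that. They do not describe usual care as free choice among tests, they give no frequency for any omitted test, and a range that starts above zero has to assume a minimum rate of displacement.

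What the objection does not remove is the inconsistency itself. Reviewers will hold records of completed screening that 2.1 scores as no screening, and the reason 2.1 gives for counting colonoscopy applies equally to other tests that patients may prefer. The conflict with 7.3.1 remains whatever the frequencies are.

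**Conclusion.** The concern holds as an unreconciled primary endpoint, with a possible bias of unknown size. On the text, patients in either arm who are known to be screened by sigmoidoscopy or Cologuard would count as unscreened, and 7.3.1 supplies two alternatives, one undefined for controls and one with no tests named.

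A bias toward the intervention arises only if omitted tests are more common in Arm 1 than in Arm 2. Displacement by mailed FIT makes that plausible, but it is not shown. The 0 to 3 points rest wholly on the assumed 1-3% and 0-100%; given that usual care is FIT-based, the true figure may be near the low end. The planned sample size is arithmetically correct and does not depend on this point. The change is worth making because it uses data largely in hand and fixes the outcome before analysis.

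**What to change.** Use one definition in 2.1, 4.1, 4.3.6 and 7.3.1, applied identically in both arms: any CRC screening test recorded on chart review within the 6-month window. List FIT, colonoscopy, flexible sigmoidoscopy and Cologuard, plus any other 3.1.3 test found (FOBT, barium enema, CT colonography). Report FIT-or-colonoscopy and FIT alone as secondary breakdowns by arm.

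If outcome data have already been examined, keep FIT-or-colonoscopy as primary and prespecify the any-test comparison by arm as a sensitivity analysis. This may well apply: section 5.1 places the sub-study in year 4 of a 6-year award, and 4.2 gives about 36 months for main-trial data collection.

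In 7.3.1, remove the FIT-kit proportion among those mailed as the Aim 1 between-arm outcome; it can stay as an Arm 2 process measure. State how Cologuard is treated at entry and as an outcome, so that the two lists agree.

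Cost: sigmoidoscopy and Cologuard need no new data. Systematic capture of the other 3.1.3 tests needs extra form options and, for charts already reviewed, a second look. The usual-care rate would rise slightly and the difference might shrink slightly, with lower power within insurance strata. The sponsor should accept that knowingly.
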